1. STUDY OVERVIEW

Background and rationale

A frequent cause of acute low back pain with radiating leg pain is lumbar disc herniation (LDH) [1]. The diagnosis of lumbar disc herniation with radiculopathy is based on history and physical examination. Muscle testing, sensory testing, test of reflexes, straight leg raising test, Lasegue sign and crossed straight leg raising tests are commonly used. To confirm the diagnosis or in cases of clinical disagreement Magnetic Resonance Imaging (MRI) is recommended [1, 2]. However, intervertebral disc herniations and protrusions are also frequently found on MRI in asymptomatic patients [3, 4].

Quantitative Sensory Pain Testing (QST) is a well-defined psychophysical method that standardizes a potentially painful stimulus and quantifies the pain response from the test subject, making it possible to investigate pain processing [5, 6].

Only few studies have investigated the clinical value of (QST) responses in patients with low back pain [7] and it has not yet been shown if the pain sensitivity is different at the level of disc herniation.

Objectives

The aim of this study is to investigate whether the segmental level of disc herniation correlates with pain thresholds in patients with lumbar disc herniation. The hypothesis is that the lowest pain threshold is at the affected level.

The specific objective is to investigate whether patients are sensitized at the level of disc herniation when examined by quantitative sensory testing, in terms of pressure pain and heat pain sensitivity.

Methods

The data from the present study were part of a prospective, 4-year observational study of patients with sciatica due to lumbar disc herniation. This study will be based on data from the baseline examination.

PICOTS

Population:

Patients were consecutively recruited between November 2018 and January 2021 from three different hospitals in Denmark; a) The Spine Center of Southern Denmark at Lillebaelt University Hospital, b) The Department of Neurosurgery at Odense University Hospital and c) The Department of Rheumatology at Frederiksberg Hospital.

Participants were thus all patients recruited in a hospital setting on referral from primary sector.

Inclusion criteria were 18+ years of age and legally competent, fluent in Danish (written and spoken), an MRI-verified disc herniation in the lumbar spine, complained of low back pain radiating below the knee or anterior thigh pain in one or both legs, pain distribution was of a dermatomal pattern, the reported average pain intensity was 3 or more on a Numerical Rating Scale (0-10 NRS), no history of previous spine surgery, surgery in general in the past 4 months, no current use of anticoagulants and/or confounding diagnoses e.g. lumbar spinal stenosis, local muscle trauma, cancer metastases, fibromyalgia and neuropathy.

Exposure:

Distance from segmental level of disc herniation: Clinical and MRI verified symptomatic level of disc herniation is labeled 0, the segmental level above and under is labeled +1 and so forth.

Outcomes:

QST measurements: Pressure Pain Threshold, kPa (PPT) and Heat Pain Threshold, °C (HPT).

Study design:

Observational cross-sectional study.

Further statistical details

Power considerations:

The current sample size had been estimated, based on previous experience and publications in the fields of QST. We had enlisted the assistance of a bio-statistician from the Institute of Regional Health Service Research. Since the project's main objective was to investigate predictor variables, there would be no hypothesis testing, and therefore no statistical basis for a power calculation. The sample size would suffice to demonstrate a statistically significant correlation at a level deemed too also be clinically relevant. The sample size was also in accordance with the previous literature in the field.

Framework:

This is an observational study assessing if patients are sensitized at the level of disc herniation when examined by QST. The data from the present study is part of a prospective, 4-year observational study of patients with sciatica due to lumbar disc herniation.

Timing of final analysis: The statistical analyses are expected to be initiated when this statistical analysis plan has been finalized and signed.

Timing of outcome assessment: (see next section)

Confidence intervals and P values: All 95% confidence intervals and P-values will be two-sided.

Multiplicity: No explicit adjustments but hierarchical testing of primary and secondary analyses as indicated by the order in the outline (Figure 2 is primary).

Statistical software: R version 4.2.2 (or newer).

2. TABULAR PRESENTATION OF TIMING OF OUTCOME MEASUREMENTS

At the first visit, the participants were assessed for eligibility to participate in the study. At this visit, the segmental level of disc herniation was recorded in the participants hospital journals and verified by MRI. Later, the participants were invited to a baseline visit, where all other data for this study was collected.

	First visit (assessment for eligibility)	Second visit (baseline)
Variables		
Segmental level of disc herniation (diagnose)	X	
Pressure Pain Threshold, kPa		X
Thermal Pain Threshold, °C		X
Patient-reported outcomes		X

3. OUTCOMES AND DATA

Data management:

In general for both Pressure Pain Threshold and Thermal Pain Threshold:

Initially, 5 test-sites were marked with a black felt-tip pen in the lumbar region. Patients identified the most painful side (right/left) and the markings were made 2 cm lateral of the spinous process of L1-L5 identified by palpation.

For each stimuli (heat and pressure) we performed the QST tests twice at each test-site. The average of the two measurements at each test-site were used for further analysis. The test order of lumbar test sites was determined a-priori as a computer-generated randomized order for each participant.

Pressure Pain Threshold:

Pressure was applied manually with a Somedic algometer type II (Hörby, Sweden, 1 cm² probe) on the marked test-sites, with a near-constant increase in pressure of 50 kPa/s until the participant indicated the pressure becoming painful by pressing an indicator button connected to the algometer.

Thermal Pain Threshold:

With a Medoc TSA-II thermode stimulator the heat pain threshold was measured on the marked test sites. The thermode stimulator had a baseline temperature of 32°C and increased 1°C/s. The patient indicated when the stimulus was perceived as becoming painful by pressing an indicator button, upon which the temperature returned to baseline (decrease 10°C/s).

Patient-Reported Outcomes:

Age
Sex
Height
Weight
Back pain intensity
Leg pain intensity
Previous pain
Use of pain medication
Physical activity
Alcohol status
Work status
Sick leave

Roland-Morris Questionnaire: Assessment of physical disability due to low-back pain.

EQ-5D Questionnaire: Assessment of health-related quality of life.

PainDetect Questionnaire: Assessment of pain and neuropathic components.

Pain drawing: A pain drawing, was filled out by pen-on-paper. This was transformed to a digital PDF, where the total area of pain was calculated as number of pixels.

Segmental level of disc herniation (diagnose)

As recorded in the participants hospital journal and verified by MRI.

Data validation:

All variables used in the analyses, will be checked for missing values, outliers and inconsistencies.

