Further statistical information related to table 2:

Data will be presented as mean with standard deviation (SD) when normally distributed or as median with interquartile range in case of non-parametric data. Normality of the data will be assessed using Q-Q plots, and histograms.

[figure not shown]
Figure 2: The association between the distance from the segmental level of disc herniation and pressure pain sensitivity (panel A) and heat pain sensitivity (panel B).

Values are least-squares means from a linear mixed models including the participant as random effect, distance from symptomatic disc herniation (5 levels; 0, 1, 2, 3, 4 segments) as fixed effect, as well as the value at 0 segments as covariate. Missing data for a specific distance will be handled implicitly by the repeated measures mixed linear models, assuming data missing at random (MAR). Error bars will indicate standard errors.

Assumptions will be checked by visual inspection of residual plots assessing the normality of residuals. In case the distributional assumptions do not hold, we will use an appropriate transformation (e.g., log-transformation in the case of right-skewed data and report the results as geometric means and geometric mean ratios), and/or, use non-parametric methods.

Figure 3: The association between the distance from the segmental level of disc herniation and pressure pain sensitivity (panel A) and heat pain sensitivity (panel B), stratified by site of symptomatic disc herniation.

Values are least-squares means from a linear mixed models including the participant as random effect, distance from symptomatic disc herniation (5 levels; 0, 1, 2, 3, 4 segments) and site of symptomatic disc herniation (5 levels, L1, L2, L3, L4, L5) as fixed effects, their interaction, as well as the value at 0 segments as covariate. Missing data for a specific distance will be handled implicitly by the repeated measures mixed linear models, assuming data missing at random (MAR).

Error bars will indicate standard errors.

SUPPLEMENTARY MATERIAL

The anticipated (predefined) supplementary material of the manuscript is illustrated below.

Supplementary file 1. This SAP

Supplementary Table 1. Patient characteristics by site of symptomatic disc herniation

Characteristics	L1 (n=)	L2 (n=)	L3 (n=)	L4 (n=)	L5 (n=)
Demographics					
Age, years					
Female, n(%)					
Body Mass Index, kg/m ²					
(...etc. as shown in Table 1)					

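### Site test order was randomized for each participant, but the Figure 2 and Figure 3 models have no test-position term, so any average drift over the sequence would cost precision, not validity

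*SAP*

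**What the plan says.** Section 3 (Outcomes and data, Data management) describes the testing. Five lumbar sites were used: "Initially, 5 test-sites were marked with a black felt-tip pen in the lumbar region". For each stimulus, "we performed the QST tests twice at each test-site", and "The average of the two measurements at each test-site were used for further analysis". On sequence it says: "The test order of lumbar test sites was determined a-priori as a computer-generated randomized order for each participant". It does not say whether the two repeats at a site were taken one after the other, in a second pass in the same order, or in a second pass in another order.

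Section 5 (Outline) specifies the Figure 2 model, which section 1 names as primary: "including the participant as random effect, distance from symptomatic disc herniation (5 levels; 0, 1, 2, 3, 4 segments) as fixed effect", and "as well as the value at 0 segments as covariate". The Figure 3 model adds herniation site and its interaction with distance. No position, order or period term appears in either model, and no sensitivity analysis on test order is described. In section 7, Table A, the item on potential confounding covariates (item 25) has a dash as its location.

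**The concern.** The primary comparison is made within a person, across neighbouring sites that are each stimulated to the pain threshold more than once. Thresholds measured this way may rise or fall as testing proceeds. The design guards against this by randomizing the order, but the analysis does not then use the randomized factor.

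Precision is what is at stake. Without a position term, an average drift counts as unexplained within-person variation and enters the standard error of every distance contrast in Figures 2 and 3. The model check in section 5 would not bring it to light, since it looks at residual plots for normality only. The SAP gives no power calculation, so nothing shows that there is precision to spare.

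**Working it through.** The SAP states no sample size, SD, effect or drift, so there is no figure of its own to reproduce.

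**Inputs.** From section 3: five sites, order randomized per participant, two measurements per site and stimulus (ten tests per stimulus), average analysed. From section 5: the Figure 2 model. Assumed: a linear average drift of *r* residual SDs per position, where the residual SD is that of the analysed site value.

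**Step 1: variance of position within a person.** Positions 1 to 5 have mean 3 and squared deviations 4 + 1 + 0 + 1 + 4 = 10, so S² = 10/4 = 2.5.

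**Step 2: effect on a contrast.** The difference in position between two randomly ordered sites has variance 2 × 2.5 = 5. Without a position term, the variance of a two-site difference within a person is therefore 2 + 5r² instead of 2, in units of residual variance. The ratio is 1 + 2.5r². It applies to any within-person contrast, because random ordering makes the sites exchangeable. The standard error is multiplied by √(1 + 2.5r²).

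**Step 3: numbers.** Information lost is 1 − 1/(1 + 2.5r²). The last column assumes a comparison with 80% power once position is in the model, two-sided 5%: Φ((1.960 + 0.842)/SE ratio − 1.960).

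| r per position | Drift from position 1 to 5 (4r) | Variance ratio | SE ratio | Extra participants needed | Information lost | Power instead of 80% |
|---|---|---|---|---|---|---|
| 0.1 | 0.4 SD | 1.025 | 1.012 | 2.5% | 2.4% | 79.0% |
| 0.2 | 0.8 SD | 1.100 | 1.049 | 10% | 9.1% | 76.2% |
| 0.3 | 1.2 SD | 1.225 | 1.107 | 22.5% | 18.4% | 71.6% |
| 0.5 | 2.0 SD | 1.625 | 1.275 | 62.5% | 38.5% | 59.4% |

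**Step 4: check in the SAP's own model.** The Figure 2 mixed model was fitted to simulated data with and without a five-level position factor. Assumed were 100 participants, a participant SD of 2 residual SDs and an illustrative mix of herniation levels, with 50 data sets per setting. The ratios below are model-based standard errors without the factor divided by those with it.

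- r = 0.3: 1.100 to 1.101 without the value at 0 as covariate, 1.095 to 1.098 with it.
- r = 0.1: 1.006 to 1.008.
- No drift: about 0.995, so the unneeded term costs about 0.5%.

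The formula and simulation agree once that cost is counted: 1.107 × 0.995 = 1.101. Mean estimates were about the same with and without the factor, as randomization implies.

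**Step 5: how the repeats were sequenced.** This is unstated and matters. With drift of r = 0.3 per single test, and S² now the variance of a site's mean place among the ten tests:

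| Second measurement | S² | SE ratio √(1 + S² × 0.09) |
|---|---|---|
| Directly after the first at each site | 10 | 1.378 |
| Second pass, same order | 2.5 | 1.107 |
| Second pass, newly randomized | 1.25 | 1.055 |
| Second pass, reversed | 0 | 1.000 |

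In the first row, moving on by one site takes two tests, so 0.3 per test is 0.6 per position: √(1 + 2.5 × 0.36) = 1.378, the same formula as in step 2.

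**The case against.** The strongest reply is that nothing here is wrong. Randomizing the order for each participant is itself the safeguard against order effects, and a precision covariate is optional. That stands, and it sets the grade of the point.

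Four stronger readings are tempting, and the SAP does not support them:

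- *The distance effect is biased, or its P-values are invalid.* Random order prevents this, and the simulation shows no shift in the estimates.
- *Chance imbalance of position across levels is a second, uncorrected defect.* Under randomization it is already part of the residual variance and hence of the standard error, so listing it separately counts the same loss twice.
- *Every primary comparison is in fact widened.* No drift is documented. Its existence, linear form and size are all assumed, and at 0.1 SD per position the loss is about 1%. A reversed second pass would already have cancelled a linear drift.
- *The adjustment is free because the list exists.* Section 3 shows that an order was generated beforehand. It does not show that the order actually followed is in the analysis data set.

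Two further limits stand. A fixed position term removes only the average drift, so drift that differs between participants remains in the residual. And if the second pass had its own order, an averaged site value has no single position, so a position factor of 1-5 is then undefined for the averages.

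**Conclusion.** The point holds as a low-cost improvement in precision, not as an error. The order was randomized per participant and the fully specified models leave it out. The planned analysis is unbiased and valid without it. The possible loss runs from about 1% to about 27% in standard error for an assumed linear drift of 0.1 to 0.5 residual SD per position. It is smaller if the second measurements were re-randomized, and nil for linear drift if they were reversed. These sizes rest on assumed drift. The SAP supplies neither a drift nor an SD with which to choose among them.

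**What to change.** Before the analysis starts:

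1. State in section 3 how the two repeats at each site were sequenced, and confirm that each participant's test order can be linked to the analysis data.
2. Add test position (1-5, as a factor) as a fixed effect to the Figure 2 and Figure 3 models, for both pressure and heat pain thresholds.
3. If the two repeats at a site were taken at different positions, fit the two single measurements instead of their average, each with its own position, and add a random effect for site within participant.

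The cost is one factor with four degrees of freedom, up to about 1% in standard error if there is no drift, and the work of linking the order list. If the order cannot be linked, the planned models can stand as they are, with a sentence saying that order was randomized but not adjusted for.

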4. PROTOCOL DEVIATIONS WITH BEARING ON THIS STATISTICAL ANALYSIS PLAN

The following details in this SAP represent deviations from the trial protocol.

Header in the protocol	Change	Reason
(currently no deviations)		

5. OUTLINE

The anticipated (predefined) outline of the manuscript is illustrated below.

Results that only will be presented in the manuscript text include:

- Number of participants included from Frederiksberg, Odense and Middelfart, respectively.
- Days on sick leave among those currently on sick leave.
- Duration of pain medication intake in days among those currently using pain medication.
- Further detailed results from the regression models visualized in figure 2 and 3.

Figure 1. Flow diagram

Anticipated plot design, illustrating potential reasons for exclusion:

[figure not shown]

Table 1. Patient characteristics

Characteristics	Total (n=)
Demographics	
Age, years	
Female, n(%)	
Body Mass Index, kg/m ²	
Back pain intensity, NRS (0-10)	
Leg pain intensity, NRS (0-10)	
Previous pain, n(%)	
Use of pain medication, n(%)	
Physical activity:	
Inactive, n(%)	
Low-impact physical activity ≥ 4 hours/week, n(%)	
High-impact physical activity ≥ 3 hours/week, n(%)	
Don't know, n(%)	
Smoking status:	
No, I don't smoke cigarettes, n(%)	
Yes, I smoke cigarettes only occasionally, n(%)	
Yes, I smoke 1 to 4 cigarettes per day, n(%)	
Yes, I smoke 5 to 14 cigarettes per day, n(%)	
Yes, I smoke 15 to 24 cigarettes per day, n(%)	
Yes, I smoke 25 or more cigarettes per day, n(%)	
Don't know, n(%)	
Alcohol status, units per week:	
0, n(%)	
1-7, n(%)	
8-14, n(%)	
15 or more, n(%)	
Don't know, n(%)	
Work status:	
Employed (eg. ordinary job, studying), n(%)	
Unemployed (eg. Senior or early retirement pension), n(%)	
Don't know, n(%)	
Sick leave, n(%)	
Questionnaires	
Roland-Morris Questionnaire	
EQ5D-3L, index score	
EQ5D-3L, VAS (0-100)	
PainDetect Questionnaire:	
Score ≥ 18, n(%)	
Score 13-18, n(%)	
Score <13, n(%)	
Pain drawing	
Pain drawing, pixels	
Segmental level of disc herniation (diagnose)	
L1, n(%)	
L2, n(%)	
L3, n(%)	
L4, n(%)	
L5, n(%)	

Further statistical information related to table 1:

Data will be presented as mean with standard deviation (SD) when normally distributed or as median with interquartile range in case of non-parametric data. Dichotomous and categorical data will be presented in proportions and/or frequency/count. Normality of the data will be assessed using Q-Q plots, and histograms.

[figure not shown]
Table 2. Quantitative Sensory Testing outcome measures

	Segment	n	Mean (SD)
Outcome			
Pressure Pain Threshold	All		
	L1		
	L2		
	L3		
	L4		
	L5		
Heat Pain Threshold	All		
	L1		
	L2		
	L3		
	L4		
	L5		

Further statistical information related to table 2:

Data will be presented as mean with standard deviation (SD) when normally distributed or as median with interquartile range in case of non-parametric data. Normality of the data will be assessed using Q-Q plots, and histograms.

[figure not shown]
Figure 2: The association between the distance from the segmental level of disc herniation and pressure pain sensitivity (panel A) and heat pain sensitivity (panel B).

Values are least-squares means from a linear mixed models including the participant as random effect, distance from symptomatic disc herniation (5 levels; 0, 1, 2, 3, 4 segments) as fixed effect, as well as the value at 0 segments as covariate. Missing data for a specific distance will be handled implicitly by the repeated measures mixed linear models, assuming data missing at random (MAR). Error bars will indicate standard errors.

Assumptions will be checked by visual inspection of residual plots assessing the normality of residuals. In case the distributional assumptions do not hold, we will use an appropriate transformation (e.g., log-transformation in the case of right-skewed data and report the results as geometric means and geometric mean ratios), and/or, use non-parametric methods.

Figure 3: The association between the distance from the segmental level of disc herniation and pressure pain sensitivity (panel A) and heat pain sensitivity (panel B), stratified by site of symptomatic disc herniation.

Values are least-squares means from a linear mixed models including the participant as random effect, distance from symptomatic disc herniation (5 levels; 0, 1, 2, 3, 4 segments) and site of symptomatic disc herniation (5 levels, L1, L2, L3, L4, L5) as fixed effects, their interaction, as well as the value at 0 segments as covariate. Missing data for a specific distance will be handled implicitly by the repeated measures mixed linear models, assuming data missing at random (MAR).

Error bars will indicate standard errors.

SUPPLEMENTARY MATERIAL

The anticipated (predefined) supplementary material of the manuscript is illustrated below.

Supplementary file 1. This SAP

Supplementary Table 1. Patient characteristics by site of symptomatic disc herniation

Characteristics	L1 (n=)	L2 (n=)	L3 (n=)	L4 (n=)	L5 (n=)
Demographics					
Age, years					
Female, n(%)					
Body Mass Index, kg/m ²					
(...etc. as shown in Table 1)					

In case of small number of participants for some sites of symptomatic disc herniation, these will be merged with a neighbouring site (e.g., merging L4 and L5).

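### The primary Figure 2 model has no term for lumbar test level, so a threshold gradient along L1-L5 can imitate or distort the effect of distance from the herniation

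*SAP*

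**What the plan says.** The objective in SAP section 1 is directional: "The hypothesis is that the lowest pain threshold is at the affected level". The exposure is an unsigned distance: "Clinical and MRI verified symptomatic level of disc herniation is labeled 0, the segmental level above and under is labeled +1 and so forth". The test sites are the same five for everyone; section 3 says the "markings were made 2 cm lateral of the spinous process of L1-L5 identified by palpation".

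Section 1 (Multiplicity) makes Figure 2 the primary analysis: "hierarchical testing of primary and secondary analyses as indicated by the order in the outline (Figure 2 is primary". Section 5 gives its model a random intercept per participant and one categorical factor: "distance from symptomatic disc herniation (5 levels; 0, 1, 2, 3, 4 segments) as fixed effect". The threshold measured at the affected level is also used on the right-hand side of the model: "as well as the value at 0 segments as covariate". Neither herniation site nor test level appears. The Figure 3 model adds "site of symptomatic disc herniation (5 levels, L1, L2, L3, L4, L5) as fixed effects, their interaction", still without test level. Table 2 describes thresholds by segment L1-L5, but no model uses segment. In the section 7 checklist, the item on potential confounders (item 25) has a dash for its location.

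**The concern.** With five fixed test sites, a participant's herniation site determines which lumbar level stands at each distance. For an L5 herniation, moving one to four segments away always means moving up the spine. For an L1 herniation it always means moving down. If the sample has more low than high herniations, or the reverse, average distance and average lumbar level move together, and the Figure 2 model attributes any difference between levels to distance.

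The primary conclusion is at stake. If thresholds happen to be lower at caudal sites and most herniations are caudal, Figure 2 would show the lowest threshold at the affected level with no sensitisation present. If the gradient runs the other way, a true effect is flattened. The plan neither states that thresholds are assumed level across L1-L5 nor checks it in the primary analysis.

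**Working it through.** The SAP states no figure for this point, so there is none to reproduce. The structure follows from the document; every kPa value rests on assumed inputs.

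**Step 1. Sites at each distance** (distance = |test level - herniation level|, levels 1-5):

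| Herniation | d=0 | d=1 | d=2 | d=3 | d=4 |
|---|---|---|---|---|---|
| L1 | L1 | L2 | L3 | L4 | L5 |
| L2 | L2 | L1, L3 | L4 | L5 | none |
| L3 | L3 | L2, L4 | L1, L5 | none | none |
| L4 | L4 | L3, L5 | L2 | L1 | none |
| L5 | L5 | L4 | L3 | L2 | L1 |

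Everyone has distances 0-2. L3 herniations have no distance 3, and only L1 and L5 herniations have distance 4.

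**Step 2. Gradient bias by hand.** Assume no sensitisation, thresholds falling 10 kPa per level from L1 to L5, and a herniation mix L1-L5 of 2/3/10/40/45%. A participant's contrast with distance 0 is 10 x (herniation level - mean level at that distance). Averaged over those who contribute:

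- d=1: 10 x (0.45 - 0.02) = 4.3 kPa, because L2-L4 herniations cancel
- d=2: 20 x (0.85 - 0.05) = 16.0 kPa
- d=3: 30 x (0.85 - 0.05) / 0.90 = 26.7 kPa
- d=4: 40 x (0.45 - 0.02) / 0.47 = 36.6 kPa

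**Step 3. The planned model.** It weights single test sites and conditions on the distance-0 value, so it differs a little from the hand figures. Simulated with between/within-participant SD 100/40 kPa, it gives:

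| Scenario | d=1 | d=2 | d=3 | d=4 |
|---|---|---|---|---|
| No effect, -10 kPa per level | 3.4 | 15.1 | 26.2 | 34.7 |
| True 30 kPa effect, +10 kPa per level | 26.8 | 15.2 | 4.3 | -4.6 |
| True 30 kPa effect, no gradient | about 30 | about 30 | about 30 | about 30 |

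Over three assumed mixes and two SD pairs, the distance-4 figure in the first row ranges from 30.4 to 36.9 kPa. With 20% of herniations at each site, the mean level tested is 3.0 at every distance and a linear gradient gives essentially no bias.

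For the error rate, a separate simulation used the same mix with an assumed n=100, SD 150/60 kPa and no true effect. The 4-df distance test at nominal 5% rejected in about 7%, 35% and 94% of runs for gradients of 0, 5 and 10 kPa per level.

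**Step 4. What corrects it.**

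- Adding herniation site alone does not. At -20 kPa per level the contrasts are 7.5, 31, 52 and 69 kPa, against 7.1, 30.6, 52.2 and 70.1 as planned.
- Adding test level but keeping the distance-0 covariate leaves 3.9-6.8 kPa at distance 4 in the 10 kPa scenario.
- Adding test level and dropping that covariate gives -0.1 to 0.5 kPa at every distance. This needs at least two herniation sites in the sample; with L5 alone, distance and level are the same variable.

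**Step 5. What the test-level term does not correct.** Suppose only L5 herniations are sensitised, by 30 kPa, with no gradient. The planned model shows a false rise from distance 1 to 4 of 8.5 kPa. The model with test level and no covariate shows 12.2 kPa. Distance 4 therefore stays unreliable in either model if profiles differ by site.

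**The case against.** **The sizes are invented.** The SAP gives no site mix, gradient or SD, and a mix symmetric about L3 removes the bias from a linear gradient. This stands: the structure is certain and the size is not. For the heat panel no figure in °C can be given either, although the structure is the same.

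**Figure 3 already helps.** In L2-L4 herniations, distance 1 averages a level above and a level below, so a linear gradient largely cancels from 0 versus 1. This also stands in part. But Figure 3 is secondary, has no test-level term and cannot separate gradient from sensitisation in L1 or L5 herniations. It does not correct the primary estimate. Nor does Table 2, because segment means mix any gradient with any sensitisation.

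**A real effect is not hidden.** A reader might infer from the second simulated row that an opposite gradient conceals sensitisation altogether. It does not: 0 versus 1 keeps 26.8 of 30 kPa. The distortion is at distances 2-4.

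**The missing-data rule is not itself a defect.** The SAP says: "Missing data for a specific distance will be handled implicitly by the repeated measures mixed linear models, assuming data missing at random (MAR". A reader might infer that treating non-existent distances this way biases the estimates. A likelihood-based model simply omits the absent rows, whatever they are called, so relabelling them changes no estimate. Likewise, the four impossible site-by-distance cells in Figure 3 contradict no figure in the SAP, which gives no degrees of freedom. Site-specific profiles alone, as in step 5, change the curve's shape but leave distance 0 lowest.

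**A 0-versus-1 contrast without adjustment is no remedy.** Correct: it carries 4.3 kPa under the gradient, slightly more than the 3.4 in the planned model. The contrast has to come from the model with test level.

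**Conclusion.** The point holds. The primary model omits test level, and with an unsigned distance and five fixed sites this confounds distance with lumbar level unless herniation sites are balanced around L3. A gradient in the same direction as the herniation mix can imitate the study hypothesis. A gradient in the opposite direction flattens a true effect and, under the assumed mix, reverses it at distance 4.

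The size is unknown. Under the assumed mix and 10 kPa per level, the false contrast grows from about 3 kPa at distance 1 to about 35 kPa at distance 4. With a common effect at every site and no gradient, the planned model is unbiased. The documents do not support saying that the primary result will be wrong, only that the plan cannot tell the two explanations apart in its primary analysis.

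**What to change.** 1. Prespecify, beside the planned Figure 2 model and for both panels, a model with test level (L1-L5) as a fixed effect and without the distance-0 covariate.
2. Name the distance 0 versus 1 contrast from that added model as the main check on the hypothesis. Every herniation site has both distances.
3. State the decision rule in advance: conclude sensitisation at the affected level only if the added model and the planned model agree. The SAP should define agreement, for example both 0-versus-1 contrasts showing the lower threshold at distance 0 with 95% confidence intervals that exclude zero.
4. Report the contributing n at each distance and treat distances 3-4 as supportive. Under the assumed mixes, 85-93% of participants contribute at distance 3 and 33-56% at distance 4, and the test-level term can enlarge distortion there if profiles differ by site.
5. Read the result beside Figure 3, noting that the L1 and L5 strata cannot separate gradient from sensitisation.

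The cost is SAP wording and one added model on data already collected. Over the assumed mixes, its standard errors are 1.02-1.05 times those without the test-level term at distance 1, and 1.3-1.9 times at distance 4. No firm pooled conclusion would be drawn at distances 3-4.
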